PROTOCOL

CO-1701-2511-3728-SACT

PROTOCOL TITLE: A SINGLE-CENTER CLINICAL STUDY TO EVALUATE THE TOLERANCE OF AN ACNE TREATMENT IN SENSITIVE SKIN SUBJECTS WITH MILD TO MODERATE ACNE VULGARIS

PROTOCOL CO-1701-2511-3728-SACT

IDENTIFICATION:

DATE & VERSION: 09 March 2017 Final Version 1.0

SPONSOR: JOHNSON & JOHNSON CONSUMER, INC.

STUDY SITES: Tennessee Clinical Research Center

[name]

PRINCIPAL [name]
INVESTIGATORS
(PIs):

STUDY MANAGER:

STUDY DIRECTOR:

DEPARTMENT
HEAD:

DESIGNATED
PHYSICIAN
REPRESENTATIVE
(DPR):

This study will be performed in compliance with International Conference on Harmonization Guidelines for Good Clinical Practice (E6).

CONFIDENTIAL: The information in this document contains trade secrets and commercial information that are privileged or confidential and may not be disclosed unless such disclosure is required by Federal or State law or regulations. Subject to the foregoing, this information may be disclosed only to those persons involved in the study who have a need to know, but all such persons must be instructed not to further disseminate this information to others. These restrictions on disclosure will apply equally to all future information supplied to you, which is indicated as privileged or confidential.

Protocol Title: A SINGLE-CENTER CLINICAL STUDY TO EVALUATE THE TOLERANCE OF AN ACNE TREATMENT IN SENSITIVE SKIN SUBJECTS WITH MILD TO MODERATE ACNE VULGARIS

Protocol identification: CO-1701-2511-3728-SACT

Date: 9 March 2017 Final Version 1.0

VERSION TRACKING

VERSION	DATE	STATE	REASON FOR CHANGE	DESCRIPTION OF CHANGE
1.0	09MAR2017	Final	N/A	N/A

SYNOPSIS

PROTOCOL IDENTIFICATION	CO-1701-2511-3728-SACT
PROTOCOL TITLE	A SINGLE-CENTER CLINICAL STUDY TO EVALUATE THE TOLERANCE OF AN ACNE TREATMENT IN SENSITIVE SKIN SUBJECTS WITH MILD TO MODERATE ACNE VULGARIS
PRINCIPAL INVESTIGATOR	[name]
STUDY SITE	Tennessee Clinical Research Center [REDACTED]
OBJECTIVE	The objective of this study is to evaluate the tolerance of a light therapy-based acne treatment in subjects with mild to moderate acne and self-reported sensitive skin over a 28-day period.
STUDY DESIGN	This is a single-center, monadic clinical trial to assess the tolerance of the test product on female and male subjects 12-40 years of age with mild to moderate acne vulgaris and sensitive skin. [REDACTED] [REDACTED] Tolerance measures will be signs and symptoms of irritation and adverse events, evaluated by the Investigator and subjects
STUDY POPULATION	Males and females, 12-40 years of age who meet the eligibility criteria of the study. [REDACTED]
SAMPLE SIZE	A sufficient number of subjects will be screened to enroll up to 45 subjects to complete with 40 total subjects.

Protocol Title: A SINGLE-CENTER CLINICAL STUDY TO EVALUATE THE TOLERANCE OF AN ACNE TREATMENT IN SENSITIVE SKIN SUBJECTS WITH MILD TO MODERATE ACNE VULGARIS

Protocol identification: CO-1701-2511-3728-SACT

Date: 9 March 2017 Final Version 1.0

INVESTIGATIONAL STUDY MATERIALS	Regimen: Cleanser, [REDACTED] [REDACTED] Acne Mask, [REDACTED]
DOSE AND MODE OF APPLICATION	ALL: Cleanser: Subjects will use twice a day to wash face, once in the morning and once at evening. Treatment (Acne Mask): Subjects will use the mask once per day, in the evening after washing/drying their face.
STUDY DURATION	This is a 28-day study comprised of 3 visits. Subjects will be assessed at Day 0 Screening/Baseline (Visit 1), Day 14 (Visit 2) and Day 28 (Visit 3).
METHODOLOGY	Evaluation of tolerance: Tolerance will be measured by signs and symptoms of irritation, [REDACTED] and adverse events. [REDACTED]
SUCCESS CRITERIA	[REDACTED]
TOLERANCE MEASURES	Signs and symptoms of irritation as evaluated by the PI based on a four-point scale, 0-3: - Erythema - Dryness/Scaling - Edema

Protocol Title: A SINGLE-CENTER CLINICAL STUDY TO EVALUATE THE TOLERANCE OF AN ACNE TREATMENT IN SENSITIVE SKIN SUBJECTS WITH MILD TO MODERATE ACNE VULGARIS

Protocol identification: CO-1701-2511-3728-SACT

Date: 9 March 2017 Final Version 1.0

	
Signs and symptoms of irritation as self-evaluated by the subject based on a four-point scale, 0-3:
 
- Burning/Stinging- Itching- Tightness/Dry Feeling
SAFETY AND ADVERSE EVENTS	
Any Adverse Event (AE), Serious Adverse Event (SAE), or Unanticipated Adverse Device Effect (UADE) related or unrelated to the investigational products must be documented as required (occurrence date, site, outcome, and assessment of causality, severity, and relatedness).
 
SAEs must be reported and relevant supportive documentation must be sent within 24h of learning of the event to the Study Manager or designee.

Protocol Title: A SINGLE-CENTER CLINICAL STUDY TO EVALUATE THE TOLERANCE OF AN ACNE TREATMENT IN SENSITIVE SKIN SUBJECTS WITH MILD TO MODERATE ACNE VULGARIS
Protocol identification: CO-1701-2511-3728-SACT
Date: 9 March 2017 Final Version 1.0

LIST OF ABBREVIATIONS

Abbreviation	Definition

1 BACKGROUND

2 OBJECTIVE(S)

The objective of this study is to evaluate the tolerance of a light therapy-based acne treatment in subjects with mild to moderate acne and self-reported sensitive skin over a 28-day period.

3 OVERALL STUDY DESIGN AND PLAN DESCRIPTION

This is a single-center clinical study to evaluate the tolerance of an acne treatment in sensitive skin subjects with mild to moderate acne. Female and male subjects 12-40 years of age with mild to moderate inflammatory acne vulgaris and self-identified as having sensitive skin will be enrolled. The principal investigator and evaluator may be the same person. The Sponsor will provide the test products.

Protocol Title: A SINGLE-CENTER CLINICAL STUDY TO EVALUATE THE TOLERANCE OF AN ACNE TREATMENT IN SENSITIVE SKIN SUBJECTS WITH MILD TO MODERATE ACNE VULGARIS

Protocol identification: CO-1701-2511-3728-SACT

Date: 9 March 2017 Final Version 1.0

4 STUDY DURATION

This study will take place over a 28-day period, with the subjects presenting to the test center for 3 visits. Visits will be at Screening/Baseline (Day 0/Visit 1), Day 14 (Visit 2) and Day 28 (Visit 3).

5 SUBJECT SELECTION AND ENROLLMENT

This study can fulfill its objective only if the required number of appropriate subjects is enrolled. The eligibility criteria are designed to select subjects for whom protocol procedures are

Protocol Title: A SINGLE-CENTER CLINICAL STUDY TO EVALUATE THE TOLERANCE OF AN ACNE TREATMENT IN SENSITIVE SKIN SUBJECTS WITH MILD TO MODERATE ACNE VULGARIS

Protocol identification: CO-1701-2511-3728-SACT

Date: 9 March 2017 Final Version 1.0

considered appropriate. All relevant medical and non-medical conditions should be taken into consideration, in addition to the inclusion/exclusion criteria, when deciding if a particular individual is suitable for this protocol. The inclusion and exclusion criteria will be reviewed by the Principal Investigator (PI) or a medically qualified designee (i.e. physician's assistant) in order to determine subject eligibility.

Prior to any review of personal data, Informed Consent and/or Assent documents should be signed.

5.1 INFORMED CONSENT AND ASSENT

The Informed Consent Document (ICD) will be read by the subject (or for a minor, his/her parent or guardian). The PI and/or his qualified designee must ensure that each study subject is fully informed about the nature and objectives of the study and possible risks associated with participation. After understanding and agreeing, the subject (or his/her legally acceptable representative) will express his/her consent to the subject's participation in the study by signing the ICD.

For studies involving children **below the age of consent**, an assent document will be prepared and presented to the subject.

The assent is a document written at an age appropriate level to inform minor subjects (i.e., under the age of consent) about the nature of the research to the extent compatible with their understanding.

Where required by national, regional, or local law, the parent or legal guardian/legally authorized representative may be required to sign an informed consent document.

If the subject qualifies for enrollment in this study they are responsible for the return of the device in the original condition in which it was provided. Failure to comply could result in forfeiture of any compensation due.

No subject will be evaluated without a signed ICD (and/or Assent Document, as applicable), which should be kept by the PI. The ICDs (and/or Assent Documents, as applicable) of subjects who are not enrolled in the study will also be kept.

One copy of the signed ICD or Assent Document must be given to the subject (or the legally acceptable representative); the subject (and/or legally acceptable representative) will remain free to withdraw this consent/assent at any moment without any negative consequence to the subject.

The ICD and Assent Document must be approved by the Sponsor and the IRB/IEC and must be in compliance with ICH GCP, local regulatory requirements, and legal requirements.

5.2 STUDY POPULATION

Individuals must meet all of the following eligibility criteria, and none of the exclusion criteria, in order to qualify and be enrolled in the study.

Protocol Title: A SINGLE-CENTER CLINICAL STUDY TO EVALUATE THE TOLERANCE OF AN ACNE TREATMENT IN SENSITIVE SKIN SUBJECTS WITH MILD TO MODERATE ACNE VULGARIS

Protocol identification: CO-1701-2511-3728-SACT

Date: 9 March 2017 Final Version 1.0

5.2.1 Inclusion Criteria

1. Subjects must read, sign, and receive a copy of the IRB-approved informed consent /assent as applicable.
2. Females and males.
3. Age: 12 to 40 years old.
4. Subjects with Fitzpatrick Skin Types of I – VI
5. Individuals who are generally in good health as determined by the investigator and study physician, based on medical history reported by the subject.
6. Acne criteria - Subjects must have a mild to moderate acne vulgaris on the face, as defined by an Investigator's Global Assessment Score of 2 or 3 using the Modified Cook's Scale as defined in section 8.2.
7. Sensitive Skin Criteria - Subjects must successfully meet the Sensitive Skin Criteria according to Sensitive Skin Inclusion Criteria questionnaire as defined in section 8.2.
8. Cutaneous Tolerance scores of 0 or 1 (no greater) in all tolerance parameters
9. Subjects must have used current consistent facial products for at least 1 month prior to study start.
10. Individuals who are able to read, speak, write, and understand English.
11. Females determined to be of child-bearing potential must agree to take a pregnancy test to confirm that they are not pregnant, and females must indicate they are not lactating nor do they intend to become pregnant during their participation in the study (subject must document their response in either the source documentation or informed consent form).

Male and Female subjects with reproductive potential must agree to practice a medically acceptable form of birth control during the study (through Week 4) or for 30 days following the last dose of investigational product whichever is later. Females must have used such birth control for at least 3 months prior to the Baseline visit.

Medically acceptable forms of birth control that may be used by the subject and/or his/her partner include:

- Established use of hormonal methods of contraception (oral, injected, implanted, patch or vaginal ring) for a minimum of 90 days prior to baseline

Protocol Title: A SINGLE-CENTER CLINICAL STUDY TO EVALUATE THE TOLERANCE OF AN ACNE TREATMENT IN SENSITIVE SKIN SUBJECTS WITH MILD TO MODERATE ACNE VULGARIS

Protocol identification: CO-1701-2511-3728-SACT

Date: 9 March 2017 Final Version 1.0

- Barrier methods of contraception with spermicide: condom or occlusive cap (diaphragm or cervical/vault caps) with spermicidal foam/gel/film/cream/suppository.
- Intrauterine device (IUD) or intrauterine system (IUS)
- Surgical sterilization (e.g., vasectomy that has been confirmed effective by sperm count check, tubal occlusion, hysterectomy, bilateral salpingectomy)
- Abstinence from heterosexual intercourse: When this is in line with the preferred and usual lifestyle of the subject. Periodic abstinence (e.g., calendar, ovulation, symptothermal, post-ovulation methods) and withdrawal are not acceptable methods of contraception.

A female subject who is postmenopausal (i.e., amenorrheic for at least 12 months prior to the Baseline visit) is not considered of reproductive potential.

5.2.2 Exclusion Criteria

Subjects with any of the hereafter criteria must be excluded from the study:

1. Has a known light or photo-sensitivity disorder.
2. Subjects with very sensitive skin, atopic dermatitis, and/or known allergies or sensitivities to ingredients contained in the cleanser (i.e. fragrance, preservatives, etc.), and/or other known medical conditions that in the opinion of the Investigator would cause them to be excluded.
3. Subjects with severe acne or acne conglobata.
4. Subjects who have pre-existing, dormant or active facial dermatologic conditions (e.g., psoriasis, rosacea, atopic dermatitis, rashes, many and/or severe excoriations, etc.) that could interfere with the outcome of the study as determined by the Investigator.
5. Female who (to the best of her knowledge) is pregnant, lactating, or planning to become pregnant during the study or within 30 days of study completion
6. Male whose female partner is (to the best of his/her knowledge) pregnant or planning to become pregnant during the study or within 30 days of study completion.
7. Subjects who report that they have used topical tretinoin (Retin-A®, Retin-A Micro®, Renova®, Adapalene, Tazarotene), Avita®, Tazorac®, Avage®, Differin®, Azelaic acid, benzoyl peroxide, Dapsone, Sodium sulfacetamide, or Epiduo or other similar prescription drug, and/or other prescription medications for acne such as Doxycycline, Minocycline, Clindamycin, Bactrim, Tetracycline, Erythromycin, and Vibramycin within 2-weeks of the study start,

Protocol Title: A SINGLE-CENTER CLINICAL STUDY TO EVALUATE THE TOLERANCE OF AN ACNE TREATMENT IN SENSITIVE SKIN SUBJECTS WITH MILD TO MODERATE ACNE VULGARIS

Protocol identification: CO-1701-2511-3728-SACT

Date: 9 March 2017 Final Version 1.0

8. Subjects who have taken Accutane or other oral retinoid within the past 6 months.
9. Subjects who report starting a new prescription medication (oral or topical) that can make skin more sensitive, cause photosensitivity, or have an effect on the skin (i.e. antibiotics, hormones (not including those used for contraception), insulin, inhaled steroids (with the exception of inhaled steroids prescribed for allergies) etc.) within 1 month prior to entry. Subjects may continue on a regular course of medication that they have been using for more than 1 month, and for which they will continue using routinely for the full course of the study, if they are stable in the opinion of the Investigator or designee.
10. Subjects using OTC topical medications on the face (excluding sunscreens, which are allowed) and/or soaps/makeup that contain topical medications (including anti-acne or antibacterial agents, topical anti-inflammatories, topical retinoids, salicylic acid etc.) within a 2-week period before the start of the study.
11. Individuals who have observable suntan, scars, nevi, tattoo, excessive hair, etc. or other dermal conditions on the face that might influence the test results in the opinion of the Investigator or designee
12. Subjects concurrently participating in any other clinical study (i.e., dermal patch, use tests, investigational drug or devices, etc.), or having participated in another facial clinical study within 30 days from the start of the study.
13. Subjects viewed by the Investigator as not being able to complete the study.
14. An individual who has any condition which in the PI's judgment makes the candidate inappropriate for study participation.
15. Individuals with a history of immunosuppression/immune deficiency disorders (including HIV infection or AIDS) or currently using immunosuppressive medications (e.g., azathioprine, belimumab, cyclophosphamide, Enbrel, Imuran, Humira, mycophenolate mofetil, methotrexate, prednisone, Remicade, Stelara.), and/or radiation as determined by study documentation.
16. Individuals with an uncontrolled disease such as asthma, diabetes, hypertension, hyperthyroidism, or hypothyroidism. Individuals having multiple health conditions may be excluded from participation even if the conditions are controlled by diet, medication, etc.
17. Individuals with any planned surgeries and/or invasive medical procedures during the course of the study.

Protocol Title: A SINGLE-CENTER CLINICAL STUDY TO EVALUATE THE TOLERANCE OF AN ACNE TREATMENT IN SENSITIVE SKIN SUBJECTS WITH MILD TO MODERATE ACNE VULGARIS

Protocol identification: CO-1701-2511-3728-SACT

Date: 9 March 2017 Final Version 1.0

18. Subjects who are related to those persons involved directly or indirectly with the conduct of this study (i.e., PI, sub-investigators, study coordinators, other site personnel, employees of Johnson & Johnson subsidiaries, contractors of Johnson & Johnson, and the families of each

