V	Dark brown; mid-eastern skin types, black hair, olive skin; Rarely burns; tans profusely
VI	Black; black hair, black eyes, black skin; Never burns; deeply pigmented

2. Investigator Global Acne Assessment – Modified Cook's Scale (Visit 1)

The following scale will be used for the global acne assessment (no half-points may be used):

0	Clear	
1	Almost Clear	
2	Mild	
3	Moderate	
4	Severe	

Protocol Title: A SINGLE-CENTER CLINICAL STUDY TO EVALUATE THE TOLERANCE OF AN ACNE TREATMENT IN SENSITIVE SKIN SUBJECTS WITH MILD TO MODERATE ACNE VULGARIS

Protocol identification: CO-1701-2511-3728-SACT

Date: 9 March 2017 Final Version 1.0

5	Very Severe
---	-------------

3. Cutaneous Tolerance Scores (Visit 1, Visit 2 and Visit 3)

Note: For enrollment (see Inclusion Criterion #8), an individual must have a score of 0 or 1.0, not higher, for all tolerance parameters at baseline.

To be evaluated by the Investigator

Erythema

0 = None

1 = Mild

2 = Moderate

3 = Severe

Dryness/Scaling

0 = None

1 = Mild

2 = Moderate

3 = Severe

Edema

0 = None

1 = Mild

2 = Moderate

3 = Severe

To be evaluated by the subject: (No half points to be used)

Burning/Stinging

0 = None

1 = Mild

2 = Moderate

3 = Severe

Itching

0 = None

Protocol Title: A SINGLE-CENTER CLINICAL STUDY TO EVALUATE THE TOLERANCE OF AN ACNE TREATMENT IN SENSITIVE SKIN SUBJECTS WITH MILD TO MODERATE ACNE VULGARIS

Protocol identification: CO-1701-2511-3728-SACT

Date: 9 March 2017 Final Version 1.0

1 = Mild	
2 = Moderate	
3 = Severe	

Tightness/Dry Feeling	
0 = None	
1 = Mild	
2 = Moderate	
3 = Severe	

5.1) Sensitive Skin Inclusion Criteria Questionnaire Parts A and B (Visit 1 only)
(see separate document)

PART A: Sensitive Skin Inclusion Criteria Questionnaire

Subjects must answer either "All of the time" or "Most of the time" to the following question:

Protocol Title: A SINGLE-CENTER CLINICAL STUDY TO EVALUATE THE TOLERANCE OF AN ACNE TREATMENT IN SENSITIVE SKIN SUBJECTS WITH MILD TO MODERATE ACNE VULGARIS

Protocol identification: CO-1701-2511-3728-SACT

Date: 9 March 2017 Final Version 1.0

Do you consider your facial skin to be sensitive?

- None of the time
- Some of the time
- Most of the time
- All of the time

PART B: Sensitive Skin Inclusion Criteria Questionnaire

Subjects must answer "yes" to at least 1 of the following 4 questions.

Question #	Question	Response

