1	In the past, have you ever experienced skin irritation (itching, burning, redness, dryness, stinging) when using topical acne treatments?	Yes or No
2	In the past, have you ever stopped using a topical acne treatment due to skin irritation (itching, burning, redness, dryness, stinging)?	Yes or No
3	Have you ever been told by a dermatologist, physician, esthetician or other professional that you have sensitive skin on your face?	Yes or No
4	When purchasing skincare products (facial cleansers, facial moisturizers, makeup, etc.), do you look for products labelled "for sensitive skin" or similar?	Yes or No

Protocol Title: A SINGLE-CENTER CLINICAL STUDY TO EVALUATE THE TOLERANCE OF AN ACNE TREATMENT IN SENSITIVE SKIN SUBJECTS WITH MILD TO MODERATE ACNE VULGARIS

Protocol identification: CO-1701-2511-3728-SACT

Date: 9 March 2017 Final Version 1.0

6) Subject Diaries (Visit 1 through Visit 3)

Subject diaries will be completed at home morning and night to record their product use every day.

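### Does excluding very sensitive skin, with no stated cut-off, undermine a tolerance study in people with sensitive skin?

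*Combined protocol and SAP*

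**What the plan says.** Section 2 of the protocol states the only objective: to "evaluate the tolerance of a light therapy-based acne treatment in subjects with mild to moderate acne and self-reported sensitive skin", over 28 days. It puts no upper limit on sensitivity.

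Inclusion criterion 7 (section 5.2.1) reads "Subjects must successfully meet the Sensitive Skin Criteria according to Sensitive Skin Inclusion Criteria questionnaire". The questionnaire, printed under section 8, has two parts. For Part A the rule is "Subjects must answer either 'All of the time' or 'Most of the time' to the following question", and the question is whether the subject considers their facial skin sensitive. Part B needs at least one yes to four questions, one of which is "In the past, have you ever stopped using a topical acne treatment due to skin irritation (itching, burning, redness, dryness, stinging".

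Exclusion criterion 2 (section 5.2.2) stands in a list that is mandatory. It covers "Subjects with very sensitive skin, atopic dermatitis, and/or known allergies or sensitivities to ingredients contained in the cleanser", and closes with other known medical conditions that the investigator thinks should lead to exclusion. No score or definition is attached to very sensitive skin.

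Four further provisions matter:

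- Section 5.2 requires all inclusion criteria and none of the exclusion criteria to be met.
- Section 5 gives the eligibility review to the investigator or a medically qualified designee and adds "All relevant medical and non-medical conditions should be taken into consideration, in addition to the inclusion/exclusion criteria". Exclusion criterion 14 separately allows exclusion for any condition that in the investigator's "judgment makes the candidate inappropriate for study participation".
- Section 8.3.2 requires the reason to be logged, and noted in the final report, for anyone who signed consent but was not enrolled. Section 5.6 leaves screen-failure data out of that report.
- Section 9 summarizes the questionnaire answers for enrolled subjects.

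**The concern.** Skin sensitivity is the trait under study, and the exclusion acts on the upper end of that same trait without a boundary. Two screeners could apply the criteria in good faith and decide differently about the same candidate.

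The study is single-arm and open-label, so no control group offsets selection at entry. The investigator may also be the evaluator (section 3). If the most reactive candidates who pass the questionnaire were turned away, the tolerance scores would tend to look better than in the population the objective names. If the report did not say how many were turned away on this ground, a reader could not tell how far the conclusion extends.

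**Working it through.** There is no stated figure to reproduce: the point does not rest on alpha, power, effect size or sample size. The check is of logic first and scale second.

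**1. Does the questionnaire contain a ceiling?** Part A has 4 answers and Part B has 4 yes/no questions.

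- Possible patterns: 4 × 2⁴ = 64.
- Qualifying patterns: 2 Part A answers × (2⁴ − 1) Part B patterns with at least one yes = 2 × 15 = 30.
- Qualifying patterns with the top Part A answer: 15.
- The extreme pattern (sensitive all of the time, four yes answers) is among the 30.

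The questionnaire has no ceiling. Separating very sensitive from sensitive is left to the person reviewing eligibility.

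**2. Does another criterion supply one?** Inclusion criterion 8 requires a baseline score of 0 or 1 on all six tolerance parameters. That limits irritation present on the day. It does not measure how readily the skin reacts, so it is not a definition of very sensitive skin.

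**3. Do the criteria contradict each other?** Inclusion 7 is a floor and Exclusion 2 is a limit. Part A asks how often the skin is sensitive, whereas *very* suggests how strongly, so the two do not measure the same thing. Where both apply, section 5.2 decides: meeting any exclusion criterion keeps the candidate out.

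**4. Would an exclusion be visible afterwards?** Consent comes before screening: "Prior to any review of personal data, Informed Consent and/or Assent documents should be signed". Anyone turned away under Exclusion 2 has therefore signed, and falls under section 8.3.2. Section 5.6 can be read alongside it as removing these people's study data, not the reason for their non-enrolment.

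**5. Can the effect be sized?** Suppose x qualifying candidates are excluded and n subjects are analysed, of whom r worsen. The percentage worsened among all n + x lies between r/(n + x) and (r + x)/(n + x), a width of x/(n + x).

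| x (assumed) | n = 40 | n = 45 |
|---|---|---|
| 0 | 0 | 0 |
| 1 | 1/41 = 2.4% | 1/46 = 2.2% |
| 4 | 4/44 = 9.1% | 4/49 = 8.2% |
| 10 | 10/50 = 20.0% | 10/55 = 18.2% |

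For comparison, the exact 95% upper limit when 0 of 40 worsen is 1 − 0.025^(1/40) = 8.8%.

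These figures do not support the concern. Every x is assumed, since the documents give none. The upper end supposes that every excluded candidate would have worsened. The same formula would apply to any exclusion criterion in any trial.

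**The case for a change.** The strongest case for a change is that general discretion does not excuse an undefined mandatory criterion aimed at the very trait being studied. In a single-arm study, who enters bears directly on the result. Section 8.3.2 asks for a reason, but its example is as broad as failing the inclusion or exclusion criteria, so a report could comply without naming Exclusion 2. The remedy would be cheap: one definition and one count.

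Part of this stands. The boundary is not visible, the direction of any selection would be towards better tolerance, and a report that named the specific criterion would be more useful than one that did not.

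It does not carry to a change, for four reasons.

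- The absence cannot be held firmly against the plan. The background section and part of the synopsis row on study population are not in the released text, and the questionnaire refers to a separate document.
- Objectives seldom restate exclusions. This one does not mention atopic dermatitis or photosensitivity either, and both are excluded.
- Removing the phrase would achieve little, because Exclusion 14 and section 5 would still let the investigator turn away the same people. Keeping it may serve a protective purpose in a population that starts at age 12. That is a trade-off for the sponsor, and the documents do not show that one side of it is wrong.
- Naming the criterion in the log and report is ordinary practice under a rule that already exists.

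**Conclusion.** The observation is accurate, but it does not call for a change. The plan leaves one adjective undefined and gives the decision to a qualified reviewer. Section 5.2 settles which criterion prevails, and section 8.3.2 already has the reason for non-enrolment reported. Nothing shows that following the plan as written would give a wrong result.

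The size of any effect is unknown. It is zero if nobody is excluded on this ground, and otherwise it depends on a number and a reaction rate that the documents do not give. That very sensitive candidates would react more to this cleanser and mask is plausible but not shown.

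The conclusion rests on two readings: that section 8.3.2 is followed for candidates turned away after consent, and that section 5.6 removes their study data and not the reason they were turned away. On that footing, the tolerance result describes people with self-reported sensitive skin whom the investigator did not judge very sensitive.
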